## 5. Statistical Analyses

### 5.1 Analysis Populations

The following populations will be used in various analyses of the data collected in the AAA 17-01 study:

1. All Enrolled Subjects - This population will consist of all enrolled Subjects. A patient is considered enrolled into the study once the Main informed consent has been signed and dated.
2. All Enrolled and Implanted Subjects - This population will consist of all enrolled and implanted Subjects. A patient is considered enrolled into the study once the Main informed consent has been signed and dated, and successfully implanted with the study device (TAMBE in the primary arm, CTAG + TAMBE in the secondary arm).
3. Uncomplicated Technical Success Eligible Population (each study arm) [Per protocol population] - This population will consist of enrolled and implanted Subjects with a follow-up visit at or after 30 days following initial TAMBE Device implant procedure. Additionally, any Subjects with an eligible technical success event, as defined in **Section 2.3.1**, even if they did not complete a follow-up visit at or after 30 days following initial procedure, will be included.
4. Clinically Significant Reintervention / Lesion Related Mortality Population (each study arm) - This population will consist of enrolled and implanted Subjects that have completed the 12 month analysis window. Additionally, any Subjects with an eligible clinically significant reintervention event, as defined in **Section 2.3.1**, even if they did not complete the necessary follow-up visit or imaging to otherwise be included in the population, will be included.
5. Secondary Effectiveness Populations (each study arm, each endpoint) - These populations will consist of enrolled Subjects with an evaluable result for the specific variable.
6. Reduced Profile VBX Population – This population will consist of the subjects in the Continued Access Phase who had been implanted with at least one reduced profile VBX device.

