## 2.4 Statistical Hypotheses

The analysis of the Uncomplicated Technical Success / Procedural Safety endpoint is intended to test the hypothesis that the safety of the TAMBE Device exceeds the performance goal of 80% technical success. This analysis will be performed on the Primary Study Arm (pararenal aortic aneurysms and adapted Crawford Type IV TAAA). The analysis of the Clinically Significant Reintervention / Lesion Related Mortality endpoint is intended to test the hypothesis that the effectiveness of the TAMBE Device exceeds the performance goal of 68% free from clinically significant reintervention / lesion related mortality events.

The hypotheses are specified as follows:

Uncomplicated Technical Success / Procedural Safety Hypothesis:

$$H_0 : P_{UCT} \leq 0.80$$

$$H_A : P_{UCT} > 0.80$$

Where  $P_{UCT}$  denotes the proportion of subjects that achieve technical success.

Clinically Significant Reintervention / Lesion Related Mortality Hypothesis:

$$H_0 : P_{CSR} \leq 0.68$$

$$H_A : P_{CSR} > 0.68$$

Where  $P_{CSR}$  denotes the proportion of subjects that achieve freedom from clinically significant reintervention.

2.5

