2.6 Sample Size Calculations

Sample size calculations were determined using PASS 13.0.8 (“Tests for One Proportion using Proportions” and “Exact” options).

The sample size calculation was motivated primarily by the Clinically Significant Reintervention Hypothesis / Lesion Related Mortality, since that would require more subjects to properly power than the Uncomplicated Technical Success / Procedural Safety hypothesis.

At least 86 are required to maintain > 80% power for the Clinically Significant Reintervention / Lesion Related Mortality Hypothesis. Assuming a 15% loss-to-follow-up rate, 102 subjects are sufficient for achieving the objective (with 81.48% power). For uncomplicated technical success, a sample size of 102 enrolled and implanted subjects (86 expected evaluable subjects) will yield a power of 93.41%. We expect the results of these hypotheses tests to be correlated, so an overall power calculation of the product of the two powers is inappropriate.

Expected accrual of subjects for the Primary Study Arm is 27 to 32 months.

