#### 5.4 Statistical Analysis of Endpoints

One-sided exact Clopper-Pearson confidence intervals for binomial proportions ( $\alpha=0.05$ ) will be constructed to test the Uncomplicated Technical Success and Clinically Significant Reintervention hypotheses in the Primary Study Arm. The null hypothesis for each endpoint will be rejected if the lower bounds of the 95% confidence interval exceeds the corresponding performance goal. This is equivalent to stating that the estimated effectiveness and safety must exceed the PG with a Type I error rate ( $\alpha$ ) of  $< 0.05$ .

Primary and Secondary Endpoints will be summarized in the Secondary Study Arm, but no hypotheses tests will be performed.

All events must meet the protocol definition.

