##### 5.4.2 Clinically Significant Reintervention / Lesion Related Mortality Events Endpoint Events

Clinically Significant Reintervention endpoint events in each study arm will consist of all enrolled Subjects experiencing an event meeting the definition in **Section 2.3.1**.

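### At the planned 15% loss, unrelated to risk, keeping early leavers with an event and dropping event-free ones does not deliver the 81.48% power stated for 102 implanted subjects

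*Combined protocol and SAP*

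**What the plan says.** SAP section 5.1, item 4, defines the population for the co-primary endpoint of clinically significant reintervention or lesion-related death at 12 months: "This population will consist of enrolled and implanted Subjects that have completed the 12 month analysis window". It then adds "any Subjects with an eligible clinically significant reintervention event", and says that such subjects, "even if they did not complete the necessary follow-up visit or imaging to otherwise be included in the population, will be included". Nothing brings in a subject who leaves early without an event.

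Section 5.4 tests the proportion with "One-sided exact Clopper-Pearson confidence intervals for binomial proportions" at 0.05. The null hypothesis is rejected if the lower limit exceeds the 68% goal in section 2.4. No censoring or other adjustment for leavers is described there.

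Section 2.6 says "At least 86 are required to maintain > 80% power" and continues: "Assuming a 15% loss-to-follow-up rate, 102 subjects are sufficient for achieving the objective (with 81.48% power". Loss is treated there as a simple reduction from 102 to 86 subjects.

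Section 1.1 makes study success depend on both co-primary endpoints. The contents list names attrition sensitivity analyses (5.6.2.5) and an analysis of missing data (5.6.2.7), but their text is redacted.

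**The concern.** A subject with an event counts whenever the event is recorded. A subject without one counts only after completing the 12-month window. If loss has nothing to do with risk and some leavers' events are recorded before they go, the population holds too many failures. The tested proportion then lies below the true 12-month freedom.

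The power in section 2.6 takes no account of this. It also takes the number of evaluable subjects as fixed at 86, whereas the number lost from 102 will vary. A device performing exactly as assumed would then miss the 68% goal more often than the plan tells the sponsor and the regulator.

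**Working it through.** **Inputs.** From the documents: goal 0.68 (2.4); one-sided exact test at 0.05 (5.4); 102 implanted, 15% loss, 86 evaluable, power 81.48% (2.6). Not in the documents: the true freedom p, because 2.5 is not readable, and f, the share of leavers' events recorded before they leave. Loss is assumed independent of risk.

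**Reproducing the plan's figure.** For n = 86 the smallest r with P(Bin(86, 0.68) ≥ r) ≤ 0.05 is 66 (exact level 0.0494). P(Bin(86, 0.80) ≥ 66) = 81.48%. Solving for p from 81.48% returns 0.80 to four digits, so p = 0.80 is used below. The enrolment figure follows from 86 / 0.85 = 101.2, rounded up to 102.

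**Fixed n.** Exact power moves in a sawtooth, and 86 is a local peak:

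| n | 85 | 86 | 87 | 88 | 89 |
|---|---|---|---|---|---|
| Power | 75.6% | 81.5% | 79.9% | 78.3% | 76.7% |

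So 86 is the smallest n reaching 80%, but slightly larger n can fall below it.

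**Power under item 4.** Let L be the loss rate.

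- Probability of being in the population: π = (1 − L) + L(1 − p)f
- Probability of being event-free, given inclusion: s = (1 − L)p / π
- n ~ Bin(102, π); given n, the event-free count is Bin(n, s); the critical value is recomputed for each n.

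Example, L = 0.15 and f = 0.5: π = 0.85 + 0.15 × 0.20 × 0.5 = 0.865; s = 0.85 × 0.80 / 0.865 = 0.786; expected n = 102 × 0.865 = 88.2; power = 68.5%.

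Results at 15% loss (type I error uses p = 0.68):

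| f | Expected proportion | Power | Type I error |
|---|---|---|---|
| 0 | 0.800 | 78.4% | 4.0% |
| 0.25 | 0.793 | 73.6% | 2.6% |
| 0.5 | 0.786 | 68.5% | 1.7% |
| 0.75 | 0.779 | 63.1% | 1.1% |

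The f = 0 row isolates the effect of a varying n: 81.5 − 78.4 = 3.1 points, unrelated to item 4. The rest of each shortfall comes from the inclusion rule.

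**Other loss rates.** For f from 0 to 0.75, power is 80.3% to 71.0% at 10% loss and 82.5% to 78.5% at 5% loss. At 5% loss and f = 0.2 it is 81.5%, so a shortfall appears only above about that value. At 2% loss power is at least 81.5% for every f.

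**What f might be.** A constant hazard with loss times spread evenly over the year gives about 0.52. One component in Table 2, the untreated clinically indicated condition, is read at the 12-month visit, which lowers f. Reinterventions, occlusions and deaths can be recorded earlier, so f = 0 is not the natural expectation either.

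**When loss is related to risk.** With stayers' 12-month risk at 20%, the item 4 proportion equals the true freedom if excluded leavers' later risk is about 21–22%. Independence implies 16%, 11% and 6% at f = 0.25, 0.5 and 0.75. Above about 21–22% the bias reverses.

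**The case against.** Much of the case on the other side stands.

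- **Loss rate.** A reader might infer that any recorded leaver's event puts power below 81.48%. That is true with 86 completers held fixed, but not in general: at low loss the figure is met. The point is therefore limited to losses near the planned 15%.
- **Unknown inputs.** f is undocumented, independence is assumed and 0.80 is back-solved. Small changes matter: at 15% loss, p = 0.81 with f = 0.25 gives 80.9%, and p = 0.82 with f = 0.5 gives 83.6%. If the planning rate was itself scored under a rule like item 4, only the varying-n part remains (78.4–79.2%).
- **Conservatism.** Keeping known failures without crediting unobserved successes works against the device. On this model no false success follows.
- **Redaction.** Sections 5.6.2.5 and 5.6.2.7 may already hold a suitable sensitivity analysis, and their text cannot be treated as absent. By their titles, though, they would not change the power in 2.6 or the primary test in 5.4.

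A reader might also infer that early lesion-related deaths are not added back, because item 4 names only reintervention events and section 2.4 says P_CSR "denotes the proportion of subjects that achieve freedom from clinically significant reintervention". That would favour the device and could inflate type I error. The documents do not support it. The add-back refers to the definition in 2.3.1, where Table 2 includes lesion-related death; 2.4 states the goal for the whole composite; and the heading of 5.4.2 reads "Clinically Significant Reintervention / Lesion Related Mortality Events Endpoint Events". The short name is used for the composite throughout.

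One defence fails. If completing the window meant only that time had passed, event-free leavers would stay in. But item 4 itself ties inclusion to the follow-up visit or imaging.

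**Conclusion.** The point holds in limited form and should be clarified; confidence is medium. At the plan's own 15% loss, with loss unrelated to risk and true freedom 0.80, section 2.6 overstates power for 102 implanted subjects. The overstatement is about 3 points at f = 0 and about 18 points at f = 0.75 (81.5 − 63.1 = 18.4). The first part needs no assumption about f. The remainder depends on an f that the documents do not give, and on the planning rate being true 12-month freedom rather than a rate already scored as in item 4.

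This is a matter of power and of an estimate biased downwards by up to about 2 points (0.800 to 0.779). The bias vanishes or reverses if the excluded leavers are at higher later risk. The documents do not support a claim of inflated type I error from the wording of the add-back, nor a claim that no attrition analysis is planned.

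**What to change.** 1. **Section 2.6.** State that 81.48% applies to exactly 86 unselected evaluable subjects, the smallest n reaching 80%. Give the power for 102 implanted subjects under item 4 as a range over loss rate and f, labelled as assumptions: 63.1–78.4% at 15% loss, 71.0–80.3% at 10% and 78.5–82.5% at 5% (f = 0.75 to 0, true freedom 0.80).
2. **Section 5.4.** Keep the exact test as primary. Add a Kaplan-Meier sensitivity estimate of 12-month freedom in all implanted Primary Study Arm subjects, with event-free leavers censored at last contact and the one-sided 95% lower limit shown against 0.68. If 5.6.2.5 or 5.6.2.7 already contains this, a cross-reference is enough.
3. **Section 5.1, item 4 (editorial only).** Say that the add-back covers any event of the Table 2 composite, including lesion-related death.

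The cost is wording in two sections and at most one extra program, with no new patients, visits or imaging. The downsides are a less favourable stated power and a sensitivity analysis that assumes non-informative censoring.

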## 2. Study Design Overview

This will be a prospective, non-randomized, two-armed, multicenter study conducted at up to forty-five (45) Clinical Investigative Sites (referred to as “sites” in the remainder of this document) in the United States and Europe. A minimum of 122 subjects, up to a potential maximum of 202 subjects, will be implanted with the TAMBE Device across two independent study arms as described below.

- Primary Study Arm – Hypothesis-driven analysis, Thoracoabdominal aneurysms (TAAAs) which are anatomically suitable for treatment with the TAMBE Device and do not require proximal extension with a CTAG Device (N=102). This arm will be limited to pararenal aortic aneurysm and adapted Crawford Type IV TAAAs.
- Secondary Study Arm – Non hypothesis-driven analysis, TAAAs which are anatomically suitable for treatment with the TAMBE Device and would require proximal extension with CTAG Device(s). This arm will include adapted Crawford Type I-III TAAAs. (N=20-100 Subjects)

Up to 65 additional subjects may be implanted in the Continued Access Phase under the Primary Study Arm only. All sites will be allowed to enroll in the Continued Access Phase, and all sites and subjects will be treated and followed in the same manner as the Core Clinical Investigation.

- The reduced profile VBX Device cohort (a subset of the Continued Access phase) will follow the TAMBE protocol: all primary, secondary, and other endpoints will be collected for these subjects as per protocol in the same manner as for the other cohorts. The Target Vessel Technical Success of the reduced profile VBX Device for each vessel will also be assessed.
- To assess the compatibility of reduced profile VBX Device as a side branch component in conjunction with the TAMBE Aortic Component (AC), the following endpoints will be summarized at a subject level:
  - Uncomplicated Technical Success at Index Procedure
  - Procedural Safety data through 30-day follow-up
  - Summary of AEs through 30-day follow-up including Type Ic and IIc Endoleaks

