**Table 1: Summary of Uncomplicated Technical Success Primary Endpoint**

Outcome	Definition (per Clinical Protocol Section 3.3)	Endpoint Time Evaluated	Final Source Data
Uncomplicated Technical Success			
Successful access and delivery	
All Gore devices are successfully tracked from the access site to the intended implantation site and released from the deliver catheter successfully without the need for unanticipated corrective intervention related to delivery.
	TAMBE Device Index procedure	Site data
Successful and accurate deployment	
Deployment of all required endovascular device components in the planned location:
 
 
- Patency of required aortic endovascular grafts with absence of device deformations (e.g., kinks) requiring unplanned placement of a non-TAMBE device component* within the endovascular graft;
 
- Patency of all branch devices with absence of device deformations (e.g., kinks) requiring unplanned placement of any non-TAMBE device component* within the branches**;
 
 
* TAMBE components include the aortic component, distal bifurcated component, iliac extenders, contralateral legs, VBX component and CTAG Device.
 
**Implantation of bare metal stents to smooth the transition from the VBX to the uncovered branch vessel will not count against technical success if the procedure otherwise meets the definition of technical success. Use of non-TAMBE devices to correct iatrogenic complications in the treated aorta or branch vessels would be considered technical failures.
	TAMBE Device Index procedure	Site Reported and CEC Adjudication 
Successful withdrawal	Successful withdrawal of the delivery systems, without a need for corrective intervention related to withdrawal	TAMBE Device Index procedure	Site data
Procedural Safety			

Outcome	Definition (per Clinical Protocol Section 3.3)	Endpoint Time Evaluated	Final Source Data
Aortic Rupture	Rupture in the stented segment of the aorta verified with direct observation or CT scan	30 days	CEC adjudication

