### 5.3 Timing of Analyses

The Uncomplicated Technical Success / Procedural Safety endpoint will be analyzed after all Subjects eligible for the Primary Arm Uncomplicated Technical Success / Procedural Safety Eligible Population have completed a follow-up visit in the 12 month follow-up window and have been on the study for 90 days.

The Clinically Significant Reintervention endpoint will be analyzed after all Subjects eligible for the Primary Arm Clinically Significant Reintervention Eligible Population have completed a follow-up visit in the 12 month window.

The primary safety endpoint will be analyzed in the Primary Study arm during the effectiveness analysis.

The Primary and Secondary Study arms will be treated independently from each other, with the secondary study arm limited to descriptive analysis.

The Sponsor will collect data that comprise the secondary endpoints throughout all study follow-up (5 years), as appropriate, in addition to their specified analysis times (see **Section 4.2**). For endpoint events that rely on CEC adjudication, site reported data will be used to assess endpoints after the 12 month analysis period.

Following accrual of the initial 102 study subjects into the Core Clinical Investigation, up to 65 additional study subjects will be enrolled and implanted to allow for Continued Access to the device after the original enrollment is complete. The initial and additional subjects will be evaluated per the Inclusion / Exclusion criteria and will employ the same follow-up schedule. All statistical inference for the PMA submission will be based on the initial 102 subjects. Data from subjects enrolled in the Continued Access cohort will be reported separately but may be pooled with the initial data for subsequent follow-up reports.

Analyses of the reduced profile VBX Device will be completed once a minimum of 10 subjects (of the Continued Access phase) are enrolled and implanted with reduced profile VBX Device and followed through 30 days

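### The Reduced Profile VBX Population is conditioned on implant, so a subject in whom every attempted reduced profile device failed is left out of the cohort's technical success summary

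*Combined protocol and SAP*

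**What the plan says.** Section 5.1 defines Population 6 in one sentence, which limits it to Continued Access subjects "who had been implanted with at least one reduced profile VBX device".

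Section 2 gives the cohort's purpose, which is to show whether the reduced profile VBX is compatible as a side branch component with the TAMBE aortic component. For that purpose "the following endpoints will be summarized at a subject level", and the first of them is "Uncomplicated Technical Success at Index Procedure". A vessel-level measure is added: "The Target Vessel Technical Success of the reduced profile VBX Device for each vessel will also be assessed".

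Table 1 (Section 2.3.1) builds technical success from access and delivery, deployment, and withdrawal. The delivery component begins: "All Gore devices are successfully tracked from the access site to the intended implantation site and released from the deliver catheter successfully".

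Section 5.3 starts the analysis of this device once "a minimum of 10 subjects (of the Continued Access phase) are enrolled and implanted with reduced profile VBX Device" and have 30 days of follow-up.

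**The concern.** Technical success asks, among other things, whether the device could be brought to its target and released. Population 6 admits a subject only after that has happened at least once with the reduced profile VBX. The population is therefore selected on part of the result it is meant to describe.

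The subject who is lost is the most informative one for a compatibility question: every reduced profile VBX tried could not be delivered or deployed, and the branch was completed with another device or abandoned. The Section 5.3 trigger is also counted on implant, so this subject neither enters the summary nor brings it closer. In a cohort that may be analysed at 10 subjects, a single case separates a report of no failures from a visible signal.

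**Working it through.** The documents give no expected success rate, performance goal or sample size calculation for this cohort, only the minimum of 10, so there is no stated figure to reproduce. The check has three steps.

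**1. Who stays and who leaves.** Apply Population 6 and Table 1 to each possible course.

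| Course at the index procedure | In Population 6? | Subject-level result under Table 1 |
|---|---|---|
| All attempted reduced profile VBX delivered and deployed | Yes | Success, if the other components are met |
| One fails, another is implanted in a different vessel | Yes | Failure |
| One fails and is replaced by a second reduced profile VBX | Yes | Failure |
| Every one attempted fails; another branch device is used | No | Failure, not in the summary |
| Every one attempted fails; the branch is abandoned | No | Failure, not in the summary |

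Only the last two rows are lost. Both are failures, so their removal cannot lower the reported rate.

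**2. Effect on the reported rate.** Let s be the successes among 10 implanted subjects and f the number of subjects with failed attempts only. The documents give no value for f, so it is assumed. As written the rate is s/10; counted by attempt it is s/(10 + f). The one-sided 95% Clopper-Pearson lower limit is the 5th percentile of a Beta(s, n − s + 1) distribution. The SAP plans that interval only for the Primary Study Arm tests, and it is borrowed here to show scale.

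| s | f = 0 (as written) | f = 1 | f = 2 |
|---|---|---|---|
| 10 | 10/10 = 100% (74.1%) | 10/11 = 90.9% (63.6%) | 10/12 = 83.3% (56.2%) |
| 9 | 9/10 = 90.0% (60.6%) | 9/11 = 81.8% (53.0%) | 9/12 = 75.0% (47.3%) |

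Ten is a minimum. If the device were used across nearly all of the 65 Continued Access places, one excluded subject would turn 64/64 = 100% into 64/65 = 98.5%.

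**3. How often a failing subject would be lost.** Suppose k reduced profile devices are attempted per subject, each failing independently with probability q. The chance that none is implanted is q^k, and the chance of at least one failure is 1 − (1 − q)^k. The share of failing subjects who leave is the ratio of the two. Neither k nor q is in the documents; q is taken from 2% to 20%.

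| k | q = 2% | q = 20% |
|---|---|---|
| 1 | 100% | 100% |
| 2 | 0.0004/0.0396 = 1.0% | 0.04/0.36 = 11.1% |
| 3 | about 0.01% | 0.008/0.488 = 1.6% |
| 4 | below 0.01% | 0.0016/0.5904 = 0.3% |

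The loss is total when one device is attempted and small when three or four are. Failures that cluster within a subject, for example through shared anatomy, would raise these shares.

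**The case against.** Several points on the other side have force.

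- A reader might infer that delivery failures in general leave the denominator. They do not. One reduced profile implant is enough to keep the subject in, and Table 1 asks for success of all the devices, so a partial failure is counted. This stands and limits the point to complete failures.
- A reader might also infer that failed vessels are dropped from Target Vessel Technical Success. The visible text gives no vessel-level denominator. It is undefined, not shown to exclude failures, and the Clinical Protocol Section 3.3 that Table 1 cites is not reproduced in the public document.
- The lost subjects need not vanish from all reporting. Continued Access runs under the Primary Study Arm and is reported separately. Population 3 retains subjects with a technical success event, and Section 5.4.1 counts events among all enrolled subjects in each study arm. A subject switched to another branch device may therefore appear as a failure there. But none of these provisions visibly returns that subject to the VBX-specific summary, and Population 6 has no event clause of its own.
- The contents list names a Section 5.6.2.3 on enrolled but not implanted subjects, whose text is redacted. It may cover abandoned procedures. Judged by its title, it would not reach a subject who received TAMBE with a different branch device.
- The SAP never says outright that Population 6 is the denominator for the Section 2 endpoints. That is an inference, though no other population is defined for this device.

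**Conclusion.** The point holds in a narrow form. A subject in whom every attempted reduced profile VBX failed is outside Population 6, hence outside the cohort's technical success summary on its natural reading and outside the count to 10. The direction is certain: the rate can only be overstated or unchanged.

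The size is not known. At the minimum cohort, one such subject would take a reported 100% down by 9.1 points and two by 16.7 points, but the counts of one and two are assumptions. Whether the case arises at all depends mainly on how many reduced profile devices are attempted per subject, which the documents do not state.

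A reader might go further and take this as a threat to the trial's conclusions. The documents do not support that. The cohort has no hypothesis or performance goal, and Section 5.3 bases all PMA inference on the initial 102 subjects, so no type I error rate or power figure moves. The change is still worth making, because it corrects a stated rule in the one summary intended to show compatibility of this device.

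**What to change.** In Section 5.1, for Uncomplicated Technical Success and Target Vessel Technical Success, define Population 6 as Continued Access subjects in whom delivery of at least one reduced profile VBX was attempted, whether or not it was implanted. State that the vessel-level denominator is all vessels attempted with that device. List every attempted-but-not-implanted case. Keep the implanted subset for follow-up measures such as endoleak and patency. The trigger in Section 5.3 can remain at 10 implanted subjects, provided the summary takes in every attempt made up to that point.

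The cost is two or three sentences. Table 1 already draws on site-reported delivery and withdrawal outcomes; the sponsor should confirm that the records also show which branch device was attempted in each vessel. The one drawback is that the reported success rate may be slightly less favourable.
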